record of any vaccine on the index date but had at least one vaccination record in the year prior to the index date; they will be assigned an index date matched to a corresponding ABRYSVO vaccinee's vaccination date and will be required to be at least 18 years of age on the matched index date. All individuals must be enrolled in (ie, not disenrolled from) VHA benefits during the 2 years prior to the index date (ie, baseline period) and have complete follow-up (ie, no disenrollment from VHA benefits, death, or receipt of RSV vaccination [for controls who may later receive any RSV vaccine only]) during the risk interval and confirmatory diagnosis window. Eligible individuals will be further classified into either the 18-59 years old age group or 60 years and older age group based on their age on the index date; contemporary vaccinated or unvaccinated controls in the 18-59 years old age group are further required to have a record for specific conditions that increase the risk for severe RSV as defined by the Centers for Disease Prevention and Control (CDC) during the baseline period (see "Subgroups" below for specific conditions).

Variables:

- Exposure: Administration of ABRYSVO will be identified based on the following:
 - o Current Procedural Terminology (CPT) code 90678, OR
 - 10 and 11-digit National Drug Codes (NDC) 0069-0207-01, 0069-0250-01, 0069-0344-01, 0069-0344-05, 0069-0344-10, 0069-0651-01, 0069-1265-10, 0069-1265-20, 0069-2465-19, 0069-2465-01, 0069-2465-10; OR
 - o Immunization records that contain data on vaccine code descriptor, vaccine manufacturer (ie, Pfizer), lot number, injection site, and date(s) of immunization.

Relevant codes will be reviewed and amended if new codes are added.

• Outcomes: The study's primary outcome, new onset atrial fibrillation, will be identified by a diagnosis code for atrial fibrillation in any setting during the 0-3 day risk interval for the primary analysis (or 0-1 day or 0-30 day risk interval for secondary analysis), or day 4-10 post vaccination control interval, followed by a confirmatory diagnosis within 30 days after the initial diagnosis and no diagnosis for atrial fibrillation or other supraventricular arrhythmia in the 2 years prior to the index date (ie, "clean window," to rule out pre-existing events). 8,9

The secondary outcome of the study will be new onset supraventricular arrhythmia, including atrial fibrillation, and will be identified in the same manner as the primary outcome.

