As of 14 July 2022 in RENOIR, there was a numerical imbalance of atrial fibrillation, a condition that causes an irregular and often fast heartbeat, with 10 events in the RSVpreF group (n=17,215) versus 4 events in the placebo group (n=17,069) within 1 month of vaccination, although the rates of overall unsolicited adverse events (AE) between RSVpreF and placebo groups were similar.^{2,3} A medical history of atrial fibrillation was reported in 60% and 50% of the cases in the RSVpreF and placebo groups, respectively, and none of the events of atrial fibrillation were considered related to RSVpreF by the investigators.³ Atrial fibrillation is the most common cardiac arrythmia, where both incidence and prevalence of atrial fibrillation have been shown to increase with age and are higher in males versus females and in those of European versus African descent.⁴ A background incidence rate of 33.9 per 1,000 person-years for incident atrial fibrillation was reported in 2007 for male versus 24.7 per 1,000 person-years for female Medicare beneficiaries 65 years of age and older.⁹ Atrial fibrillation is part of a broader group of supraventricular arrhythmia which are relatively common cardiac rhythm disturbances typically occurring in repetitive bouts.

Additionally, Pfizer's pivotal Phase 3 clinical trial, MONeT (RSV IMmunizatiON Study for AdulTs at Higher Risk of Severe Illness; Study C3671023 evaluating the safety, tolerability, and immunogenicity of ABRYSVO in adults aged 18 and older at risk of developing severe RSV-associated LRTD is ongoing. The MONeT trial consists of two substudies – a double-blind randomized study among 681 adults aged 18 to 59 years old with certain chronic medical conditions (substudy A) and an open-label study among approximately 200 adults who are immunocompromised (substudy B). Positive top-line safety and immunogenicity results were announced for substudy A in April 2024 and for substudy B in August 2024. 5,6 Based on the inferred efficacy from the Phase 3 MONeT trial, the FDA approved ABRYSVO for the prevention of LRTD caused by RSV in individuals 18 through 59 years of age who are at increased risk for LRTD caused by RSV on 22 October, 2024. 7

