9.2.1. Inclusion Criteria

Three cohorts will be defined for the main analyses.

- A. A cohort of individuals who received ABRYSVO will form the ABRYSVO cohort and must have:
 - A record for at least one dose of ABRYSVO in the study period from 31 May 2023 (or earliest date of vaccine availability for the indicated population) to 31 May 2026; the date of ABRYSVO vaccination will define the index date for this cohort
 - o No record of an RSV vaccine from a manufacturer other than Pfizer
- B. A cohort of individuals who did not receive ABRYSVO but received another vaccine will form the contemporary vaccinated control cohort and must have:
 - A record for another vaccine (eg, influenza vaccine, COVID-19 vaccine, and other pre-specified vaccines such as shingles, hepatitis B listed in Section 9.3.3) within 30 days of a corresponding ABRYSVO vaccinee's vaccination date; the control's index date will be the date of the control's non-RSV vaccine
 - No record for any RSV vaccine on the index date or in the baseline period (ie, 2 years prior to the index date)
 - Individuals in the vaccinated control cohort who go on to receive an RSV vaccine following their index date will be censored at the time of RSV vaccination. If the RSV vaccine is ABRYSVO, these individuals will contribute to the ABRYSVO cohort starting from the date of ABRYSVO receipt.
- C. A cohort of individuals who did not receive ABRYSVO or another vaccine on the index date but had at least one vaccination record in the year prior to the index date will form the contemporary unvaccinated control cohort and must have:
 - No record for any RSV vaccine on or within 30 days of the index date or in the baseline period (ie, 2 years prior to the index date)

- No record for any other vaccine (eg, those listed in Section 9.3.3) on or within 30 days of the index date
 - This cohort will be assigned an index date matched to a corresponding ABRYSVO vaccinee's vaccination date. If the vaccination is associated with a healthcare encounter (ie, inpatient [IP] or outpatient [OP] visit), the unvaccinated control will be required to have a healthcare encounter within 30 days of the assigned index date, and the date of the healthcare encounter will be set as the index date for the unvaccinated control.

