 - Individuals in the unvaccinated control cohort who go on to receive an RSV vaccine following their index date will be censored at the time of RSV vaccination. If the RSV vaccine is ABRYSVO, these individuals will contribute to the ABRYSVO cohort starting from the date of ABRYSVO receipt.
- o Regular use of preventive medical care, defined as at least one vaccination record between 365 to 31 days prior to the index date.

In addition, individuals in all cohorts must meet the following inclusion criteria to be eligible for the study:

- At least 2 years of continuous enrollment in (ie, no disenrollment from) VHA benefits (ie, the baseline period) prior to the index date
- Complete follow-up (ie, no disenrollment from VHA benefits, death, or receipt of RSV vaccination [for controls who may later receive any RSV vaccine only]) during the risk interval and confirmatory diagnosis window (eg, 34 days of complete follow-up for 0-3 days primary risk interval plus 30-day confirmatory diagnosis window; or 32 days or 61 days for secondary analysis with 0-1 days and 0-30 days risk intervals plus 30-day confirmatory diagnosis window, respectively).

Based on age on the index date, eligible individuals will be further classified into the following two age groups with the following additional inclusion criteria:

- 18-59 years old age group
 - o 18-59 years of age on the index date
 - o For individuals in cohorts B and C, a record for specific conditions that increase the risk for severe RSV as defined by the CDC during the baseline period, identified as those with chronic cardiovascular disease, chronic lung or respiratory disease, end-stage renal disease or dependence on hemodialysis or other renal replacement therapy, diabetes mellitus with complications, neurologic or neuromuscular conditions causing impaired airway clearance or respiratory muscle weakness, chronic liver disease, chronic hematologic

conditions, severe obesity, moderate or severe immune compromise, residence in a nursing home, or other chronic medical conditions or risk factors that a health care provider determines would increase the risk for severe disease due to viral respiratory infection (eg, frailty); list of conditions may be updated to align with the most current CDC definition at the time of data analysis¹⁹

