9.7.2.2. Comparison with Contemporary Controls

Average treatment effect among the treated (ATT) weighting will be used to ensure baseline comparability between the ABRYSVO vaccinated cohort vs. contemporary vaccinated control cohort and between the ABRYSVO vaccinated cohort vs. contemporary unvaccinated control cohort. ATT weighting creates a "pseudo-population" in which the distribution of covariates is, on average, the same in each cohort. ⁶⁸ Specifically, ATT weights will be calculated to allow for estimation of the average treatment effect among individuals receiving ABRYSVO.⁶⁹ This approach will be taken to ensure that inference from the analysis will be applicable to this population. Individuals receiving ABRYSVO will receive an ATT weight of one. Individuals not receiving ABRYSVO will receive an ATT weight equal to the odds of receiving ABRYSVO conditional on their demographic and clinical characteristics as of the index date, which will be calculated based on the propensity score (PS). The PS is defined as an individual's probability of receiving ABRYSVO, conditional on observed baseline covariates, and will be calculated using a logistic regression model. The logistic regression model will include the cohort variable (ie, ABRYSVO vs. vaccinated or unvaccinated control) as the dependent variable, and the independent variables will include variables deemed clinically important and baseline covariates that have standardized differences ≥10% between the two cohorts. Specifically, ATT weights will be PS/(1-PS) for individuals with no record of ABRYSVO. The distribution of weights will be examined to assess extreme values, and truncation will be considered if necessary.

Weighted Cox regression with robust standard errors to account for within-subject correlation will be conducted to compare the risk of safety events between cohorts. Hazard ratios and corresponding 95% CIs will be summarized.

9.7.2.3. SCRI Design using the Conditional Poisson Regression for Comparison to Post-vaccination Control Intervals

SCRI design with post-vaccination control time period will include cases (ie, individuals vaccinated with ABRYSVO who experience safety events following vaccination) who have at least 41 days (or 38 days or 91 days for secondary analysis) of enrollment post-index to compare the incidence of safety events occurring in the risk interval following vaccination with the incidence of safety events occurring during the post-vaccination control interval.

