To reduce possible outcome misclassification, confirmatory diagnosis of atrial fibrillation and supraventricular arrhythmia will be required within 30 days of the initial diagnosis. In PFIZER CONFIDENTIAL

addition, chart review adjudication will be used to ensure a high PPV for identifying atrial fibrillation. If the PPV is not considered high enough, the algorithm used to identify incident atrial fibrillation using codified data may be updated in subsequent analyses.

The study population has been kept as broad as possible in order to capture safety events that occur among all individuals vaccinated with ABRYSVO. However, individuals who ever had a record of RSV vaccine from a different manufacturer are excluded to ensure that safety signals are not attributable to different RSV vaccines. Thus, the study results are not generalizable to patients who received RSV vaccines from different manufacturers.

The VHA CDW provides a range of benefits, including its comprehensive structure, large number of variables, and electronic accessibility. The VHA CDW also includes EHR data that include structured fields and open fields (such as physician notes, which will be used for case validation, as needed). Importantly, the VHA CDW retains electronic immunization records that include manufacturer name and lot numbers, facilitating the identification of brand-specific vaccines, such as ABRYSVO. Moreover, the VHA CDW data are updated on a daily basis.

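### In the 18-59 group a recorded CDC risk condition is required of controls but not of ABRYSVO recipients, so recipients without a record have no comparable controls and the cohort hazard ratio may be biased, more likely downward, by an unknown amount

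*Protocol*

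**What the plan says.** Section 9.2.1 defines three cohorts: A (ABRYSVO recipients), B (vaccinated controls) and C (unvaccinated controls). For ages 18-59 it adds: "For individuals in cohorts B and C, a record for specific conditions that increase the risk for severe RSV as defined by the CDC". The population paragraph of the Abstract repeats the rule, again for controls only: "contemporary vaccinated or unvaccinated controls in the 18-59 years old age group are further required to have a record for specific conditions".

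Cohort A needs a record of an ABRYSVO dose in the study period and no record of another manufacturer's RSV vaccine. The criteria common to all cohorts add 2 years of enrollment and complete follow-up. Section 9.2.2 excludes baseline arrhythmia and missing date of birth. None of these asks a recipient aged 18-59 for a recorded condition. The indication enters the cohort A criteria only through the start date ("or earliest date of vaccine availability for the indicated population").

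On weighting, section 9.7.2.2 says "Individuals receiving ABRYSVO will receive an ATT weight of one" and "Specifically, ATT weights will be PS/(1-PS) for individuals with no record of ABRYSVO". Section 9.9 adds: "The study population has been kept as broad as possible in order to capture safety events that occur among all individuals vaccinated with ABRYSVO".

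**The concern.** A cohort comparison needs controls of the same kind as the treated people whose effect is being estimated. Every 18-59 control has at least one listed condition on record; a recipient need not. ATT weighting leaves recipients as they are and reweights only the controls, so a pattern that no control has cannot be reproduced by any choice of weights. For recipients without a record, the positivity assumption behind ATT weighting fails.

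The list includes chronic cardiovascular and lung disease and end-stage renal disease. If recipients without a record have less AF than those with one, the controls carry too high a background rate and the hazard ratio is pulled down. In a safety study that is the direction that can hide a signal.

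**Working it through.** **1. Is the rule asymmetric?** Yes. The Abstract and section 9.2.1 both confine it to controls, and nothing in 9.2.1 or 9.2.2 imposes it on cohort A.

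**2. Can a recipient lack a record?** The protocol leaves room for it.
- The test is a record in the VHA baseline period, not the condition itself. Section 9.9 accepts that clinical information may be incomplete because of care outside the VHA.
- The Medicare linkage meant to fill that gap is for the 60+ group only (sections 9.2.3 and 9.9). The 18-59 group has a priority group 1 subgroup, which reduces missed care but does not align the criterion.
- The list ends with risk factors judged by a provider. A recipient can be vaccinated on that judgement with no listed code on file.

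**3. What did the sizing assume?** Section 9.5.1 starts from 9 million enrollees, 1 million of them with prior AF, 56% aged 60 or over (so 44% younger), 85% continuously enrolled, and 11% or 29% with a risk condition.
- (9M - 1M) × 0.44 × 0.85 × 0.11 = 329,120
- (9M - 1M) × 0.44 × 0.85 × 0.29 = 867,680

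This reproduces the stated 330,000 to 868,000. The eligible pool is thus counted as if everyone aged 18-59 had a condition, which cohort A does not enforce.

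**4. Effect on the hazard ratio.** Let λ be the background AF rate in people with a record, f the share of recipients without one, and r their background rate divided by λ. Without a vaccine effect the recipients' rate is λ[(1-f) + f·r]. If the weighted controls have rate λ, then

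observed HR = true HR × [1 - f(1-r)].

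The protocol gives neither f nor r. Assumed values:

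| f | r | multiplier | true HR 2.0 reads |
|---|---|---|---|
| 0 | any | 1.00 | 2.00 |
| any | 1 | 1.00 | 2.00 |
| 5% | 0.5 | 0.975 | 1.95 |
| 20% | 0.5 | 0.90 | 1.80 |
| 30% | 0.25 | 0.775 | 1.55 |
| 20% | 1.25 | 1.05 | 2.10 |

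**5. Effect on power.** Inputs from section 9.5.1: 4.4 per 1,000 person-years, 4-day window, 4:1 controls, one-sided alpha 0.05, 80% power. The background risk is m0 = 0.0044 × 4/365.25 = 0.0000482. With unpooled Poisson variance,

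n = (1.645 + 0.842)² × (HR + 1/4) / [m0 × (HR - 1)²].

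This gives 288,688 at HR 2.0 (stated 286,730) and 898,139 at HR 1.5 (stated 892,049), both within 1%. At the stated 286,730 recipients,

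power = Φ{(HR - 1)·√(N·m0)/√(HR + 1/4) - 1.645}, with N·m0 = 13.8.

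- HR 2.00: 79.8%
- HR 1.95: 77%
- HR 1.80: 0.80 × 3.717/√2.05 - 1.645 = 0.43, so 67%
- HR 1.55: 45%

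These ignore any further loss of precision from weighting.

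**6. Balance.** Take an indicator for any listed condition, which is a composite and not itself a listed covariate. All controls score 1 and a share 1-f of recipients do. The standardized difference is f/√[f(1-f)/2] = √[2f/(1-f)], whatever the weights: 32% at f=5% and 71% at f=20%. It passes the 10% limit of section 9.7.1 once f exceeds 0.01/2.01, about 0.5%.

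**The case against.** The strongest reply is the label. Approval at these ages is for "individuals 18 through 59 years of age who are at increased risk for LRTD caused by RSV", the qualifying list is wide, and restricting controls looks like an attempt to mirror the indication. If nearly all recipients have a record, f is near 0 and the bias is negligible. That limits the likely size. It does not remove the defect, because the protocol never checks for a record in recipients. If all do have one, applying the rule to them removes nobody.

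A reader might infer that the hazard ratio is certainly biased downward, and by a lot: with 20% to 40% of recipients lacking a condition and a two- to three-fold AF ratio, a null effect would read 0.90 to 0.73. The protocol does not support this, for three reasons.
- It gives neither the share without a record nor the AF rate by condition. An r above 1, for instance in sicker people treated elsewhere, would push the ratio upward.
- Recipients with a real but unrecorded condition should not be given the rate of people with no condition. If half of f is under-recording at ratio 1 and half has no condition at ratio 0.5, then r = 0.5 × 1 + 0.5 × 0.5 = 0.75, and at f=20% the multiplier is 0.95, not 0.90.
- The propensity score can use individual comorbidities, frailty, the Charlson index and hospitalizations, and so move controls towards milder disease. The downward shifts in the table are then upper bounds. Individual covariates may still balance on average, which is all that section 9.7.2.2 claims; only the joint pattern of no recorded condition cannot be matched.

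The scope is also limited. The primary objective is descriptive, and the SCRI uses recipients only (section 9.1.2). Comparative analyses run only when adequately powered: 286,730 recipients would be 33% of 868,000 or 87% of 330,000. Pooling is conditional (section 9.7). Standardized differences and negative control outcomes might reveal an imbalance but would not repair it.

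**Conclusion.** The point stands as an asymmetric entry rule that leaves any 18-59 recipient without a recorded condition outside the support of the controls. Bias is possible and more likely downward, given the kinds of condition listed, but neither its direction nor its size is established. It requires f above 0 and r different from 1. Under the assumed values it ranges from none, through 2.5% (f=5%, r=0.5), to 10% (f=20%, r=0.5), the last two being maxima if weighting shifts controls towards milder disease. It touches the 18-59 cohort comparisons with both control groups and any pooled comparison that contains them. It does not touch the descriptive incidence, the 60+ analyses or the SCRI.

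**What to change.** In section 9.2.1 and the Abstract, require of cohort A the same record of a CDC-defined condition in the 2-year baseline period, for the 18-59 and pooled comparative cohort analyses only. State in section 9.7.2.2 that the ATT target is then 18-59 recipients with a recorded condition. Keep all 18-59 recipients in the descriptive incidence, so that the breadth described in section 9.9 is retained there. Report how many recipients the rule removes and how many AF events they had; this gives f and a first view of r.

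The cost is a narrower target population, including the loss from the comparison of indicated recipients whose condition was coded outside the VHA, and some precision, both in proportion to f. The required sample sizes do not change, but they must then be met by recipients with a record.

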9.2.2. Exclusion Criteria

Individuals meeting any of the following criteria will be excluded from the study:

- Individuals with a record for atrial fibrillation or other supraventricular arrhythmia during the baseline period
- Individuals with missing date of birth

For the analyses using the SCRI design, a subset of eligible individuals from the ABRYSVO cohort that experienced atrial fibrillation or other supraventricular arrhythmia in the risk or control intervals will be included.

9.2.3. Subgroups

Safety surveillance may be conducted for subgroups of interest as applicable to each age group, including, but not limited to the ones described below.

The following subgroups will be analyzed for the 18-59 years old age group and the 60 years and older age group:

- Individuals in VA priority group 1; These individuals have either the highest levels of service connected disability (≥50% disabling), are considered unemployable, or have received the medal of honor. Individuals categorized as priority group 1 are the highest priority for VHA care. This will ensure that the individual is more likely to receive all of their care from a VA facility;
- Females enrolled in the VHA (pending sufficient sample size);

• Individuals with co-administration with other vaccines (ie, influenza vaccine, COVID-19 vaccine, or other pre-specified vaccines [eg, shingles, hepatitis B] listed in Section 9.3.3) on the same day.¹⁸

The following subgroups will be analyzed for the 60 years and older age group only:

- Individuals with specific conditions that increase the risk for severe RSV as defined by the CDC during the baseline period; list of conditions may be updated to align with the most current CDC definition at the time of data analysis (see Section 9.2.1);
- Different age groups defined by age on the index date, eg, 60 to 69 years, 70 to 79 years, ≥80 years;
- Individuals enrolled in the VHA with dual coverage who are also identified in the Centers for Medicare & Medicaid Services (CMS) Medicare administrative claims data, which will be linked to the Corporate Data Warehouse (CDW) to supplement the data for a more complete evaluation of healthcare encounters.

Additional subgroups of interest may be assessed as additional information becomes available from ongoing clinical trials, Vaccine Adverse Event Reporting System (VAERS), and other sources that will inform the ABRYSVO safety profile.

